8.6.2.1.1 Time Period and Frequency for Collecting AE and SAE Information

Nonserious AEs will be collected from the time of the first dose of IP through the date of the follow-up or last visit, and at the time points specified in the Schedule of Activities (Section 1.2).

The Reference Safety Information in Sections 5.6.1 and 5.6.2 of the IB should be used to determine the expectedness of SAEs for expedited reporting. Following the participant's written consent to participate in the study, all SAEs, whether related or not related to study drug, must be collected, including those thought to be associated with protocol-specified procedures.

All SAEs that occur from the time ICF is signed to 30 days after the final dose of the study drug must be reported to PRA Drug Safety. After that time, only SAEs deemed by the investigator to be related to the study drug or a study procedure should be reported.

If applicable, SAEs must be collected that relate to any later protocol-specified procedure.

- The investigator must report any SAE that occurs after this time period and that is believed to be related to study treatment or protocol-specified procedure.
- Medical occurrences that begin before the start of study treatment but after obtaining informed consent will be recorded on the appropriate section of the eCRF.
- All SAEs will be recorded and reported to sponsor or designee within 24 hours, as indicated in Appendix 2.
- The investigator will submit any updated SAE data to the sponsor or designee within 24 hours of this being available.

Investigators are not obligated to actively seek AEs or SAEs in former study participants. However, if the investigator learns of any SAE, including a death, at any time after a participant has been discharged from the study, and he/she considers the event reasonably related to the study treatment or study participation, the investigator must promptly notify the sponsor.

The method of evaluating intensity and assessing causality of AEs and SAEs and the procedures for completing and reporting/transmitting SAE reports are provided in Appendix 2.

8.6.2.1.2 Method of Detecting AEs and SAEs

AEs can be spontaneously reported or elicited during open-ended questioning, examination, or evaluation of a participant. In order to prevent reporting bias, participants should not be questioned regarding the specific occurrence of one or more AEs.

8.6.2.1.3 Follow-up of AEs and SAEs

Nonserious AEs should be followed to resolution, or stabilization, or reported as SAEs if they become serious (Appendix 2).

Follow-up is also required for nonserious AEs that cause interruption or discontinuation of study treatment and for those present at the end of study treatment as appropriate.

All identified nonserious AEs must be recorded and described on the nonserious AE page of the eCRF. Completion of supplemental eCRFs may be requested for AEs and/or laboratory abnormalities that are reported/identified during the course of the study.

After the initial AE/SAE report, the investigator is required to proactively follow each participant at subsequent visits/contacts. All SAEs will be followed until resolution, until the condition stabilizes, until the event is otherwise explained, or until the participant is lost to follow-up (as defined in Section 8.4.6.3).

Further information on follow-up procedures is given in Appendix 2.

8.6.2.1.4 Regulatory Reporting Requirements for SAEs

Prompt notification by the investigator to the sponsor of SAEs is essential so that legal obligations and ethical responsibilities towards the safety of participants and the safety of a product under clinical investigation are met.

An investigator who receives an investigator safety report describing SAEs or other specific safety information (eg, summary or listing of SAEs) from the sponsor will file it along with the IB and will notify the IRB/EC, if appropriate according to local requirements.

The sponsor or designee will report AEs to regulatory authorities and IECs according to local applicable laws including European Directive 2001/20/EC and FDA CFR 21 CFR Parts 312 and 320. A SUSAR (Suspected, Unexpected Serious Adverse Reaction) is a subset of SAEs and will be reported to the appropriate regulatory authorities and investigators following local and global guidelines and requirements.

8.6.2.1.5 *Pregnancy*

If following initiation of the study treatment, it is subsequently discovered that a participant is pregnant or may have been pregnant at the time of study exposure, including during at least 5 half-lives after product administration, the investigator must immediately notify the medical monitor/designee of this event and complete and forward a Pregnancy Surveillance Form to BMS Designee within 24 hours of awareness of the event and in accordance with SAE reporting procedures described in Appendix 2.

If the participant becomes pregnant study treatment must be discontinued immediately. Please contact the medical monitor or designee within 24 hours of awareness of the pregnancy.

Follow-up information regarding the course of the pregnancy, including perinatal and neonatal outcome and, where applicable, offspring information must be reported on the Pregnancy Surveillance Form.

Any pregnancy that occurs in a female partner of a male study participant should be reported to sponsor or designee. In order for sponsor or designee to collect any pregnancy surveillance information from the female partner, the female partner must sign an ICF for disclosure of this

information. Information on this pregnancy will be collected on the Pregnancy Surveillance Form.

8.6.2.1.6 Laboratory Test Result Abnormalities

The following laboratory test result abnormalities should be captured on the nonserious AE eCRF page or SAE Report Form electronic, as appropriate. Paper forms are only intended as a back-up option when the electronic system is not functioning.

- Any laboratory test result that is clinically significant or meets the definition of an SAE
- Any laboratory test result abnormality that required the participant to have study treatment discontinued or interrupted
- Any laboratory test result abnormality that required the participant to receive specific corrective therapy

It is expected that wherever possible, the clinical rather than laboratory term would be used by the reporting investigator (eg, anemia vs low hemoglobin value).

8.6.2.1.7 Potential Liver Injury

Wherever possible, timely confirmation of initial liver-related laboratory abnormalities should occur prior to the reporting of a potential DILI event. The study treatment discontinuation criteria are provided in Section 8.4.6.1. All occurrences of potential DILIs, meeting the defined criteria, must be reported as SAEs (Appendix 2 for reporting details).

Participants who meet criteria for DILI should have relevant laboratory testing (eg, ALT, AST, and INR levels) repeated at least weekly until abnormalities have resolved. Tests should be repeated within 3 days; then, every 3 days until reversal is noted; and then, every week until normalization. The investigator should make every effort to determine if any other cause for the liver test abnormalities is present.

8.6.2.1.8 Other Safety Considerations

Any significant worsening noted during interim or final physical examinations, ECG, X-ray filming, or any other potential safety assessment required or not required by protocol should also be recorded as a nonserious or serious AEs, as appropriate, and reported accordingly.

8.6.2.2 Overdose

An overdose is defined as the accidental or intentional administration of any dose of a product that is considered both excessive and medically important. All occurrences of overdose must be reported as SAEs (Appendix 2).

In the event of an overdose, the investigator should do the following:

- 1. Contact the medical monitor immediately.
- 2. Closely monitor the participant for AEs/SAEs and laboratory abnormalities until BMS-986263 can no longer be detected systemically.
- 3. Obtain a plasma sample for PK analysis within 2 days from the date of the last dose of study treatment if requested by the medical monitor (determined on a case-by-case basis).
- 4. Document the quantity of the excess dose as well as the duration of the overdosing in the eCRF.

Decisions regarding dose interruptions or modifications will be made by the investigator in consultation with the medical monitor based on the clinical evaluation of the participant.

[figure not shown]
8.6.2.3 Physical Examinations

Schedules for physical examinations are provided in Schedule of Activities (Section 1.2). Complete and/or abbreviated physical examinations may be performed by a Doctor of Medicine (MD) or equivalent, or someone who is authorized to perform the examinations by training and has been delegated this task by the principal investigator.

[figure not shown]
Full physical examinations will be performed at screening and Days 85 and 253 in Part 1 and screening and Days 85, 169, and 253 in Part 2. A full examination will include general appearance, skin, head, eyes, ears, nose, throat, neck, thyroid, chest/lungs, heart, abdomen, lymph nodes, extremities, height, and body weight.

Abbreviated physical examinations will be performed at the other time points (Schedule of Activities; Section 1.2), which will include an abdominal exam, assessments of ascites and hepatic encephalopathy, and symptom-focused assessments. An abbreviated examination may note any changes in the participant's condition (body systems) since the last assessment and does not preclude examination of any of the other body systems as clinically indicated. Every effort should be made to ensure the same evaluator will complete the examination for each participant at all visits throughout the study. Documentation of who performed the examination is to be recorded in source notes.

8.6.2.7 Clinical Safety Laboratory Assessments

[figure not shown]
Investigators must document their review of each laboratory safety report. A central laboratory will perform the analyses and will provide reference ranges for these tests. Results of clinical laboratory tests performed on Day -1 must be available prior to dosing.

Hematology, serum chemistry and urinalysis assessments are listed below:

Table 11 Hematology, Chemistry, Urinalysis, Assessments

Hematology		
 CBC PT PTT INR Blood Chemistry	WBC (absolute)HemoglobinHematocritMCV	 MCH concentration Red cell distribution width Platelet count
 AST ALT Total bilirubin Direct bilirubin ALP LDH GGT Creatinine Urinalysis	 Creatinine clearance Creatine kinase BUN Uric acid Glucose PTH Total protein Albumin sodium 	 Potassium Chloride Carbon dioxide Calcium Phosphorus Glomerular filtration rate
 pH Specific gravity Protein 	GlucoseKetonesLeukocyte esterase	 Nitrite Creatinine Microscopic examination (only to follow-up abnormal findings)
HbA1C Serology/viral load	HCV viral load (RNA)	HbcAb and HBV viral DNA if HbcAb-positive.

8.6.2.8 Imaging Safety Assessments – DXA

DXA (femur, hip, and lumbar spine) will be performed at the time points indicated in Schedule of Activities (Section 1.2). DXA is to be scheduled at least 5 days ahead of Day 1 (Randomization) to allow adequate time for results to be analyzed.

Image acquisition guidelines and submission processes will be outlined in the IM025006 Imaging Manual, to be provided by the central imaging facility. The clinical sites will be trained in imaging procedures prior to scanning the first study participant. All images will be submitted to the central imaging facility for assessment of the BMD.

Adequacy of DXA should be confirmed by the central imaging facility prior to randomization. The site will be informed of quality issues or the need to repeat scanning from the central imaging facility.

Any incidental findings of potential clinical relevance that are not directly associated with the objectives of the protocol should be evaluated and handled by the investigator as per standard medical/clinical judgement.

8.6.3 Pharmacokinetics

Blood for PK samples for Part 1 will be drawn according to the sampling schedule shown in Table 12. For Part 2, blood for PK samples will be drawn according to the sampling schedule shown in Table 13.

Samples from participants randomized to placebo will not be analyzed.

Table 12 Pharmacokinetic Sampling Schedule for BMS-986263 in Part 1

Day ^a	Event	Time ^h (Relative to BMS-986263 Dose) Hour: Min	BMS-986263 Blood Sample for plasma PK
1	pre-infusion	00:00 ^{b,} ■	X
1	mid-infusion	00:30°	X
1	end-of-infusion	00:00 ^d	X
1	postinfusion	01:00 ^{e,} ■	X
4 (± 1 day)	postinfusion	72:00 ^f	X
8	pre-infusion	00:00 ^b ,■	X
8	mid-infusion	00:30°	X
8	end-of-infusion	00:00 ^d	X
8	postinfusion	01:00 ^e ,■	X
15	pre-infusion	00:00 ^b ,■	X
29	pre-infusion	00:00 ^b ,■	X
29	mid-infusion	00:30°	X
29	end-of-infusion	00:00 ^d	X
29	postinfusion	01:00 ^e ,■	X
36	pre-infusion	00:00 ^b	X
43	pre-infusion	00:00 ^b ,■	X
43	mid-infusion	00:30°	X
43	end-of-infusion	00:00 ^d	X
43	postinfusion	01:00 ^e ,■	X
46 (± 1 day)	postinfusion	72:00 ^f	X
50	pre-infusion	00:00 ^b	X
57	pre-infusion	00:00 ^{b,} ■	X
78	pre-infusion	00:10 ^b ,■	X
78	mid-infusion	00:30°	X
78	end-of infusion	00:00 ^d	X
78	postinfusion	01:00 ^e ,∎	X
85	postinfusion	168:00 (7 days) ^f .■	X
99	postinfusion	504:00 (21 days) ^f	X

PK = pharmacokinetics

^a The days for PK sampling are indicated in the Schedule of Activities (Section 1.2).

^b Time is relative to the start of infusion. Samples may be collected up to 120 minutes prior to the start of the infusion.

^c Time is relative to the start of infusion. Samples should be collected ± 3 minutes within specified timeframe. If infusion is administered at a modified rate, the timing of collection of this sample should correspond to the middle of the modified infusion duration of the total administered dose.

- ^d Time is relative to the end-of-infusion. Samples should be collected -2 minutes within specified timeframe. This sample should be taken immediately prior to stopping the infusion. If the end-of-infusion is delayed to beyond the nominal infusion duration, the collection of this sample should also be delayed accordingly.
- ^e Time is relative to the end-of-infusion. Samples should be collected ± 3 minutes within specified timeframe.
- $^{\rm f}$ Time is relative to the end-of-infusion of the previous dosing day. Sample may be collected \pm 1 day at the PK visit on Day 4 and Day 46.

Pharmacokinetic Table 13 Sampling Schedule for BMS-986263 in Part 2

Day ^a	Event	Time (Relative to BMS-986263 Dose) Hour: Min	BMS-986263 Blood Sample for plasma PK
1	pre-infusion	00:00 ^b ,■	X
1	mid-infusion	00:30°	X
1	end-of-infusion	00:00 ^d	X
1	postinfusion	01:00 ^e ,■	X
4 (± 1 day)	postinfusion	72 :00 ^f	X
15	pre-infusion	00:00 ^b	X
29	pre-infusion	00:00 ^{b,} ■	X
29	mid-infusion	00:30°	X
29	end-of-infusion	00:00 ^d	X
29	postinfusion	01:00 ^e ,■	X
43	pre-infusion	00:00 ^b ,∎	X
43	mid-infusion	00:30°	X
43	end-of-infusion	$00:00^{d}$	X
43	postinfusion	01:00 ^{e,} ■	X
46 (± 1 day)	postinfusion	72 :00 ^f	X
57	pre-infusion	00:00 ^b	X
71	pre-infusion	$00:00^{\rm b}$	X
85	pre-infusion	00:00 ^{b,} ■	X
85	mid-infusion	00:30°	X
85	end-of-infusion	00:00 ^d	X
85	postinfusion	01:00 ^{e,}	X
99	pre-infusion	00:00 ^b	X
113	pre-infusion	00:00 ^b	X
127	pre-infusion	00:00 ^b	X
141	pre-infusion	00:00 ^b	X
141	mid-infusion	00:30°	X
141	end-of-infusion	00:00 ^d	X
141	postinfusion	01:00°	X
155	pre-infusion	00:00 ^b	X
169	postinfusion	336:00 (14 days)	X

PK = pharmacokinetics

^a The days for PK sampling are indicated in the Schedule of Activities (Section 1.2).

^b Time is relative to the start of infusion. Samples may be collected up to 120 minutes prior to the start of the infusion.

^c Time is relative to the start of infusion. Samples should be collected ± 3 minutes within specified timeframe. If infusion is administered at a modified rate, the timing of collection of this sample should correspond to the middle of the modified infusion duration of the total administered dose.

- ^d Time is relative to the end-of-infusion. Samples should be collected -2 minutes within specified timeframe. This sample should be taken immediately prior to stopping the infusion. If the end-of-infusion is delayed to beyond the nominal infusion duration, the collection of this sample should also be delayed accordingly.
- $^{\rm e}$ Time is relative to the end-of-infusion. Samples should be collected ± 3 minutes within specified timeframe.
- ^f Time is relative to the end-of-infusion. Sample may be collected ± 1 day at the PK visit on Day 4 and Day 46.

9. STATISTICAL CONSIDERATIONS

9.1 Sample Size Determination

This study will enroll a total of 60 participants in Part 1 of the study, randomized via IRT in a 1:2:1 ratio to receive 45 mg BMS-986263 QW, 90 mg BMS-986263 QW, and placebo QW. The sample size for Part1 is not based on formal statistical justification. Part 1 of the study is designed for estimation purposes; no statistical testing will be performed. A 95% confidence interval (CI) for the primary endpoint of proportion of participants with \geq 1 stage improvement in fibrosis on biopsy after 12 weeks of treatment and odds-ratios between treatment groups will be utilized for this purpose.

In Part 2, approximately 120 participants will be randomized via IRT in a 1:1:1:1 ratio to receive 45 mg BMS-986263 Q2W, 90 mg BMS-986263 Q2W, 90 mg BMS-986263 Q4W, or placebo Q2W in a double-blind manner. The primary endpoint for Part 2 is the proportion of participants with ≥ 1 stage improvement in fibrosis on biopsy after 24 weeks of treatment. For this portion (Part 2) of the study, it is anticipated that approximately 10% of the participants will discontinue (dropout) early from study treatment. Participants who discontinue early or otherwise have the result from the liver biopsy missing will be considered a "nonresponder" for the evaluation of the primary endpoint and other binary endpoints based on liver biopsy.

The response rates for the primary liver biopsy endpoint for the 4 treatment groups in Part 2 are assumed to be as follows: placebo Q2W - 20%, 90 mg BMS-986263 Q4W - 30%, 45 mg BMS-986263 Q2W - 35%, and 90 mg BMS-986263 Q2W - 50%. With these assumptions, using a 1-sided 0.05 level of significance, there will be 80% power to detect a trend using a Cochran Armitage trend test in the primary endpoint among the 4 treatment groups with n = 30 in each group.

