- g. Participants with known metallic fragments in the body
- h. Employment history that involves exposure to welding

The above list should not be used as a substitute for local clinical standards of care. The ultimate decision to perform any scan should rest with the site radiologist, the investigator, and the standard set by the IEC.

Lifestyle Restrictions:

Participants should not consume ≥ 7 units/week of alcohol during the study. One drink "unit" or one standard drink is equivalent to 12 ounces of beer, 4 ounces of wine, or 1 ounce of hard liquor.

NUMBER OF PARTICIPANTS:

It is planned that approximately 180 male and female participants will be evaluable for analysis. In Part 1, approximately 60 participants will be randomized in a 1:2:1 ratio to receive 45 mg BMS-986263 QW, 90 mg BMS-986263 QW, or placebo QW. In Part 2, approximately 120 participants will be randomized in a 1:1:1:1 ratio to 45 mg BMS-986263 Q2W, 90 mg BMS-986263 Q2W, or placebo Q2W. If a higher than expected proportion of study participants discontinue from the study prior to the evaluation of the primary endpoint, the sponsor may choose to enroll additional participants to ensure an adequate number of participants are available for evaluation of the primary endpoint.

STUDY TREATMENT(S):

Test Product and Reference Therapy, Dose and Mode of Administration:

BMS-986263 (45 mg or 90 mg) or placebo will be administered as an IV infusion according to the treatment schedule outlined in the Schedule of Activities (Section 1.2).

BMS-986263 has the potential to treat liver fibrosis as it combines an HSP47 siRNA with a formulation designed to target the HSP47 siRNA to HSCs.

Please refer to the Pharmacy Manual for complete information on BMS-986263 and placebo storage, handling and infusion, and exact volumes and instructions on the preparation of study treatment infusion.

Study Treatment Infusion Rate

The study medication should not be infused at a duration lesser than 60 minutes. The infusion rate may be modified by the investigator based on clinical discretion and/or the participant's previous tolerance of the infusion, including any infusion reactions that may have occurred in the past. In addition, the investigator may choose to pause the infusion depending on the participant's clinical condition and history.

Of note, while the rate of infusion can be modified as described above; no reductions or modifications of the total dose to be administered are allowed.

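### Does the 80% power for Part 2 ignore the 10% dropout that the same section expects?

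*Protocol*

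**What the plan says.** Protocol 9.1 builds the Part 2 sample size in this order:

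1. About 120 participants are randomised 1:1:1:1, and the primary endpoint is an improvement of at least one fibrosis stage on biopsy after 24 weeks.
2. On attrition, "it is anticipated that approximately 10% of the participants will discontinue (dropout) early from study treatment".
3. On scoring, "Participants who discontinue early or otherwise have the result from the liver biopsy missing will be considered a" non-responder for the primary endpoint and the other binary biopsy endpoints.
4. The rates come next: "The response rates for the primary liver biopsy endpoint for the 4 treatment groups in Part 2 are assumed to be as follows", namely 20% on placebo, 30% on 90 mg Q4W, 35% on 45 mg Q2W and 50% on 90 mg Q2W.
5. The power statement then rests on these assumptions: "using a 1-sided 0.05 level of significance", "there will be 80% power to detect a trend using a Cochran Armitage trend test" with 30 per group.

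Three other places bear on the point. Protocol 9.2 and 9.3.1.2 put the primary analysis on the mITT population, meaning everyone randomised who received at least one dose. Protocol 8.4.6.4 and the synopsis (Number of Participants) let the sponsor enrol more people if discontinuation runs above expectation. The same synopsis paragraph says "It is planned that approximately 180 male and female participants will be evaluable for analysis", which equals the 60 + 120 to be randomised. The SAP provided covers Part 1 only and adds nothing to the Part 2 power.

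**The concern.** A sample-size section that names a dropout rate usually does something visible with it: it inflates the number randomised or discounts the effect. Here neither appears. The 120 randomised are exactly 4 × 30, and the power is quoted at 30 per group. If 20/30/35/50% describe participants who actually have a Week 24 biopsy, the scoring rule pulls each arm down by a tenth, the differences between arms shrink with it, and the test has less power than stated. The synopsis seems to point the same way, because it calls the full randomised number evaluable.

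At stake would be the only power figure given for the Part 2 primary test. The type II error would be about 26% rather than 20%.

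**Working it through.** **Inputs (Protocol 9.1).** Rates p = 0.20, 0.30, 0.35, 0.50; n = 30 per group; one-sided alpha 0.05, so z = 1.645. The protocol gives no trend scores. I assume x = 0, 1, 2, 3 in the order of the assumed rates, with mean 1.5 and Σ(x − 1.5)² = 5. The calculation is unstratified, because the documents give no rates by fibrosis stage.

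**Formula (normal approximation, Cochran-Armitage).**

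- T = n Σ(x − x̄)p
- V0 = n p̄(1 − p̄) Σ(x − x̄)²
- V1 = n Σ(x − x̄)² p(1 − p)
- Power = Φ[(T − 1.645 √V0) / √V1]

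**Step 1: the plan's own figure.**

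- T = 30 × (−0.300 − 0.150 + 0.175 + 0.750) = 30 × 0.475 = 14.25
- p̄ = 0.3375; V0 = 30 × 5 × 0.3375 × 0.6625 = 33.54; √V0 = 5.79
- V1 = 30 × (0.3600 + 0.0525 + 0.0569 + 0.5625) = 30.96; √V1 = 5.56
- Power = Φ[(14.25 − 9.53) / 5.56] = Φ(0.85) = 80.2%

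Simulation gives 80.7%. Scores proportional to dose per four weeks (0, 1, 1, 2) also give 80.2%. The stated 80% reproduces.

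**Step 2: every rate cut by a tenth.** The rates become 18%, 27%, 31.5% and 45%.

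- T = 0.9 × 14.25 = 12.825
- p̄ = 0.30375; √V0 = 5.63; √V1 = 5.46
- Power = Φ[(12.825 − 9.26) / 5.46] = Φ(0.65) = 74.3%

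Scores 0, 1, 1, 2 give 74.2%. The 74% is therefore correct arithmetic, but only if the stated rates are rates before dropouts are scored.

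**Step 3: which rates does the section give?** The endpoint is defined first, then the dropout rate, then the rule that a dropout is a failure on that endpoint, and only then the rates for that endpoint. Nothing describes them as rates among completers or among those biopsied. Read as written, 20/30/35/50% are proportions of everyone in the arm, with dropouts already counted as failures. The implied rates among participants with a biopsy are each stated rate divided by 0.9:

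| Arm | Stated (all in the arm) | Implied among those biopsied |
|---|---|---|
| Placebo Q2W | 20% | 22.2% |
| 90 mg Q4W | 30% | 33.3% |
| 45 mg Q2W | 35% | 38.9% |
| 90 mg Q2W | 50% | 55.6% |

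Multiplying the last column by 0.9 returns the stated rates, and Step 1 then applies unchanged: 80.2% with 30 randomised per group and 10% dropout. Cutting the stated rates again would subtract dropout twice.

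**Step 4: is inflation missing?** Inflation is needed when dropouts leave the denominator. Here they stay in it: the mITT set keeps every dosed participant, and a missing biopsy is scored, not excluded. With rates stated for that endpoint, 30 is the right n. The option to enrol more only when discontinuation exceeds expectation fits an expected 10% that is already covered.

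**Step 5: the synopsis wording.** Under this scoring rule a dosed participant without a biopsy still has a primary outcome. Calling about 180 participants evaluable therefore does not contradict randomising 60 + 120.

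**The case for a change.** The strongest reply is that no sentence says the rates are net of dropout. If they were meant for participants with a biopsy, power is 74.3% at 30 per group, and 80% would need about 36 per group (144 in total). The net reading also commits the sponsor to more optimism than is visible on the page: about 56% response among biopsied participants at the top dose, not 50%. Finally, the provision for extra enrolment speaks of having enough participants available for evaluation, which suggests that dropouts are not evaluable and sits awkwardly with 180 evaluable out of 180 randomised.

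Part of this stands. The section is not explicit, and one clause would have settled it. But silence does not favour the lower figure: nothing says the rates are before dropout either, and the order of the text points the other way. The 74.3% also needs an input the protocol does not give, a 10% loss in each arm, since 9.1 states only about 10% of participants. The looser use of evaluation in the enrolment provision is a matter of wording and does not alter how the primary endpoint is scored.

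**Conclusion.** Not a problem. The stated 80% follows from the stated inputs (80.2%) and, on the literal reading of Protocol 9.1, already allows for 10% dropout scored as non-response. The six-point fall to 74.3% appears only if the assumed rates are taken as rates before dropout, a reading the text does not state and its order does not favour. Restating the power as 74% would put a wrong figure into the protocol on the literal reading.

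This conclusion rests on reading the rates as those of the endpoint just defined, on the trend scores assumed above (the two plausible sets agree), and on an unstratified approximation to a stratified test. The lack of an explicit statement that the rates are net of the 10% is a missing detail. It affects no test, analysis population, participant number or conclusion.
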